Secondary and exploratory analysis will rely on data collected at 3-, 6-, and 12-month follow-up surveys that will permit analysis of secondary outcomes of: (1) durability of treatment effect at 52 weeks (e.g., continuous retention in OBOT with buprenorphine); (2) engagement with social services; and (3) longitudinal engagement with the proposed intervention (up to 26 weeks). For these analyses, we will use generalized linear mixed effects regression to model binary outcomes indicating longitudinal engagement in 26-week treatment (yes/no) and continuous retention in buprenorphine treatment at 3-, 6-, and 12-months (yes/no) with no more than a 28-day gap in receiving an active buprenorphine prescription over each period. These models will include a participant-specific random intercept to account for the repeated-measures structure of the data.

Methodological Considerations and Alternatives: To assess whether randomization was successful, we will compare the distribution of demographic characteristics, PhenX consensus measures, medical/psychiatric history, technology use patterns, and risk behavior variables (see *Data Collection*) by intervention arm. Variables contributing to baseline imbalance will need to be included as adjustment variables in regression models.

Missing Data and Sensitivity Analysis will rely on ensuring that the model assumption of non-informative study dropout or missing at random is reasonable and avoid potential bias, we will compare dropout rates between intervention groups as well as other measured variables, e.g., medical/psychiatric history, technology use patterns, and risk behavior variables. If there is empirical evidence of nonrandom dropout, we will model the dropout event using available factors to identify and estimate their influence. To meet missing at random model assumption, variables that predict dropout will be included as auxiliary variables via multiple imputation.

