Health-Related Quality of Life (HRQoL) will be measured using the validated Patient-Reported Outcomes Measurement Information System (PROMIS)—Preference (PROPr) instrument. PROMIS (including PROPr) was developed using item response theory (IRT), with support from the NIH. Because of its IRT foundation, PROPr is more flexible, and improves upon common deficiencies of alternative HRQoL instruments. The PROPr scoring system uses the respondent's scores for each of the following domains to calculate a HRQoL index value that represents the general US population's preference for a respondent's health state: Cognitive Function—Abilities, Depression, Anxiety Fatigue, Pain Interference, Pain Intensity, Physical Function, Sleep Disturbance, and Ability to Participate in Social Roles and Activities. HRQoL values produced by PROPr range from -0.022 to 1, where 0 represents death, 1 represents perfect health, and values below 0 represent states perceived to be worse than death. The HRQoL value is then used to calculate regression-adjusted QALYs per study arm as our team and others have done in similar studies. 103,122–125,238

Healthcare, Non-Medical and Other Services. The utilization of healthcare services by participants will be measured using study data and the Timeline Follow-Back (TLFB)¹⁹¹ methodology via the Non-study Medical and Other Services (NSMOS) form. Healthcare services will include inpatient, outpatient, telehealth, and ED services; opioid use disorder treatment

medications, and residential and outpatient substance use disorder treatment days; hospital detoxification days; and mental health treatment visits. The reliability and validity of self-reported data is well established over recall periods similar to those in this proposal 196,204,239–241. Non-medical and other resources required to determine the costs from the state policymaker and societal perspectives (e.g., recidivism, workplace productivity, etc.) will be collected via the NSMOS form, Addiction Severity Index – *Lite* (ASI), and other study instruments. The NSMOS, ASI, and other study instruments have been successfully used by the economic team in prior economic evaluation studies 122,124,125, and is currently in-use in numerous clinical trials of substance use disorder treatments, including those associated with the NIDA Clinical Trials Network (CTN) and Justice Community Opioid Innovation Network (JCOIN) 120,123,242.

Aim 3 Data Analysis

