Inclusion criteria: 1) ≥18 years of age; 2) fluent in English; 3) self-reported non-prescription opioid use <30 days prior to consent; 4) provision of informed consent; 5) planned stay in NYC ≥12 month; 6) Black and/or Latinx race/ethnicity; 7) positive urine toxicology for opioids per EMR records or study staff administered random saliva drug testing; 8) diagnosis of OUD per the Diagnostic and Statistical Manual of Mental Disorders-5 (DSM-5); 9) self-reported interest in initiating buprenorphine in primary care, or elsewhere; and 10) must have a mobile phone data plan.

Exclusion criteria: 1) inability to comprehend text content written at a 3rd grade reading level; and 2) physical or visual disability preventing mobile phone use

Retention Plan for PWUO in Aim 1 centers around methods previously utilized by the MPIs in their prior NIH-funded studies that have yielded rates of study retention above 80%. Components of our planned participant retention strategy include: 1) Completion of a locator form at baseline and at all follow-up visits to assist in locating participants in the event of a missed study visit (e.g., participant's current address, email, phone numbers, contact information for at least 3 trusted friends/family); 2) soliciting consent to contact the participants' 3 trusted contacts as well as health care staff at the study site hospital; 3) providing timely study visit telephone call and text reminders; and 4) coordination with trained study staff to conduct outreach to assist with in-person searchers at their homes, shelters, or other community sites. On the day of a missed study visit, the participant will receive two phone calls and two text messages at different times of the day. If there is no response within 24 hours, mailed follow-up reminder letters and/or emails will be sent encouraging contact with research staff. If there is no contact within 72 hours, the participant's locators will be contacted at varying hours. Study staff will also check for incarceration status using http://www.vinelink.com/, and google.com, intellius.com, and spokeo.com for updated contact information. All contact with participants and/or their locators will be documented in the Participant Communication Log. No information from this form will be used in data analyses. Participants will be offered incentives to respond inperson or via telephone to ensure improved retention during scheduled study follow-up visits.

Projected attrition rates

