Patient Cohort. In this study we will use the FDA definition of serious adverse events (SAEs). Both adverse events (AEs) and SAEs will be systematically assessed at each clinic visit for the patientparticipants. We do not anticipate SAEs are AEs related to the use of text messaging which is our intervention. Any SAE, whether or not related to study intervention, will be reported to the IRB and NIDA. The initial SAE report will be followed by submission of a completed SAE report to both institutions. In the event that a patient either withdraws from the study or the investigator decides to discontinue a patient due to SAE, the patient will be monitored by the investigator via ongoing status assessment until 1) a resolution is reached, for example the problem requiring hospitalization has resolved or stabilized with no further changes expected, 2) the SAE is determined to be clearly unrelated to the study intervention, or 3) the SAE results in death. SAEs would include hospitalization (for example as the result of an opioid overdose, which is not uncommon among high-risk OUD patients) or opiate overdose resulting in death. The study team will conduct, at a minimum, an annual Data Safety Board meeting to review all SAEs. All PI's will attend this meeting. If more than 2 SAEs occur in any year, meetings of the board will be increased in frequency. All observed SAEs (again, regardless of relation to the study intervention) will be periodically reported to NIDA. A summary of the SAEs that occurred during the previous year will be included in the annual progress report to NIDA. The MPIs will be responsible for monitoring and recording both AEs and SAEs.

Provider and administrator study participants providing in-depth interview data. We do not anticipate any AEs or SAEs for the clinician and administrator participants undergoing virtual indepth interviews (Aim 2). For this sample we will also adopt the FDA definition of an SAE. AEs and SAEs for the provider and administrator sample will be handled exactly as specified for the PWUO participant cohort.

Standard AE definitions will include the following:

Adverse event: Any untoward or unfavorable medical occurrence in a human subject, including any abnormal sign (for example, abnormal physical exam or laboratory finding),

symptom, or disease temporally associated with the subject's participation in the research, whether or not considered related to the subject's participation in the research.

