Appropriately qualified and trained study personnel will elicit participant reporting of AEs and SAEs at each study visit designated to collect AEs. Adverse events assessment and collection will begin when the participant signs the informed consent form and follow-up will continue through 30 days after the last study visit. Study personnel will obtain as much information as possible about the reported AE/SAE to complete the AE/SAE forms and will consult as warranted.

All AEs and SAEs are reported to the WCG IRB according to their reporting guidelines. Standard reporting, within 7 calendar days of the site becoming aware of the event, is required for reportable AEs. Expedited reporting (within 24 hours of their occurrence and/or site staff's

knowledge of the event) is required for reportable SAEs (including death and life-threatening events).

Reporting mechanisms of IRB actions to NIDA

Any IRB action that impacts study protocol or that has no impact on study protocol will be reported to NIDA program official within 24 hours of notification from IRB. This will be done via email and followed up with official documentation. Any changes to study protocol that is not an IRB action, but a sole decision of the PI will also be communicated to NIDA program *prior* to the implementation of the change.

Plan for Incidental Findings Management

If an incidental finding is discovered during screening procedures, the participant will be notified and given a proper referral to a service provider. Moreover, [name] will draft and approve the training of study staff protocols for the referrals to OUD treatment and primary care services. In case of an adverse event as a result of study participation, the contact PI will be responsible for reporting to the IRB of record.

Conflict of interest

Any conflicts of interest will be reported to the IRB.

Responsibility for data and safety monitoring

The MPIs ([name], [name] and [name]) will be responsible for monitoring the study.

Frequency of DSM reviews

As indicated above, on a monthly basis, the MPI will meet with the study team to review notes and assess issues of community concern about potential disclosure issues or reports of adverse consequences.

Content of DSM report

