The following will be included in the DSM report: 1) brief description of protocol, 2) baseline socio-demographic characteristics, 3) retention and disposition of study participants, 4) quality assurance issues, 5) AEs, 6) SAEs, 7) efficacy, 8) suggested and actual protocol changes

Interim Data Analysis Plans

Interim analyses will be performed to evaluate safety. At each DSMB meeting, all SAEs will be evaluated and compared between study groups. If SAEs differ between groups in a manner determined to be related to study procedures, the study will be paused. Decisions to pause the study will be made by the independent DSMB.

In addition to consistent monitoring by members of the research team for adverse events, quarterly interim analyses of the survey data, quality control checks, and study activities will also be performed to ensure that all participant data are protected and there are no adverse events or harm to participants. During this review, validity and integrity of the data will also be monitored.

References

- [name] JD, Nunes Jr EV, Novo P, et al. Comparative effectiveness of extended-release naltrexone versus buprenorphine-naloxone for opioid relapse prevention (X: BOT): a multicentre, open-label, randomised controlled trial. *Lancet*. 2018;391(10118):309-318.

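### No required vital-status check for participants lost to follow-up, so deaths among them can be missed in the between-arm SAE comparison

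*Combined protocol and SAP*

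**What the plan says.** **Safety capture.** Under Collection and Reporting of SAEs and AEs, the plan states "Both adverse events (AEs) and SAEs will be systematically assessed at each clinic visit for the patientparticipants" and, later in the section, "study personnel will elicit participant reporting of AEs and SAEs at each study visit designated to collect AEs". The collection window opens at consent and "follow-up will continue through 30 days after the last study visit". The same section gives "opiate overdose resulting in death" as an example of an SAE and requires expedited reporting, within 24 hours, of reportable SAEs (death included) once site staff know of them.

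**Use.** Under Interim Data Analysis Plans, at each DSMB meeting "all SAEs will be evaluated and compared between study groups", and a difference judged related to study procedures pauses the study.

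**Tracing.** The Retention Plan for Aim 1 provides for calls, texts, letters, contact with three trusted people, in-person outreach, an incarceration look-up and web searches for new contact details. These contacts go into a communication log, of which the plan says "No information from this form will be used in data analyses".

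**Discontinuation.** Participant Discontinuation, Follow-up says that a cause will be established. The list has one code for failure to return with no contact (code 1) and another for death (code 9).

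**Analysis.** Aim 1 uses Cox regression assuming non-informative censoring. If dropout appears non-random, "variables that predict dropout will be included as auxiliary variables via multiple imputation". Aim 3b refers to recommended approaches to missing data without naming one. The utility scale is described as one "where 0 represents death, 1 represents perfect health". No section says how a death enters the linkage, retention or QALY analysis.

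**The concern.** Participant report at visits finds most kinds of SAE in people who attend. It cannot find a death, which becomes known only if a contact, a record or an outreach worker discloses it. The plan has places where such news could surface but no step that requires anyone to look for it. A participant who dies and is not recognised as dead therefore falls under code 1 and does not reach the SAE file.

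This matters more here than in most behavioural trials. Overdose death is the trial's stated rationale, the plan itself expects overdose hospitalizations in this population, and the pause rule can act only on events that have been found. Detection by chance may also differ by arm. Arm 1 has peer text check-ins three times a week for 26 weeks, whereas control participants have only the scheduled visits and the tracing of missed ones. Silence, or news of a death, could surface more readily in arm 1 and make it look less safe than control. That is an inference from the design, not something the plan reports.

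**Working it through.** **1. How many people fall outside visit-based capture.** Projected attrition rates gives losses of 20%, 15% and 10%, with 200, 170 and 153 of 252 retained at months 3, 6 and 12. Applying the losses in sequence:

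- 252 × 0.80 = 201.6
- 201.6 × 0.85 = 171.4
- 171.4 × 0.90 = 154.2

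These agree with the table to within rounding at each step, and also with the 202, 172 and 155 under Subject Payment. Not seen at month 12:

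- 252 − 153 = 99, or 39.3%
- 252 − 155 = 97, or 38.5%

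**2. Whether any planned route requires a vital-status check.**

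| Route | Could it reveal a death? | Is a check on vital status required? |
|---|---|---|
| Participant report at visits | No | No |
| Locators and outreach after a missed visit | Yes, if disclosed | No; the aim is re-contact |
| Web searches | By chance | No; incarceration and contact details only |
| EHR and chart audit | Yes, if recorded | No; utilization and treatment entry, with much EHR use exploratory |
| Discontinuation cause | Code 9 exists | A cause is to be established, but no source is named |
| SAE reporting duty | Once staff know | Depends on staff learning of it |

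Every route depends on someone happening to learn of the death. The continued status assessment under Collection and Reporting of SAEs and AEs does not fill the gap, because it is written for withdrawal or discontinuation due to an SAE, not for loss to follow-up.

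**3. Illustrative size.** The documents give no mortality rate and no detection rate, so both are assumptions.

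- Deaths in 252 over 12 months at 1%, 2%, 4% and 6%: 2.5, 5.0, 10.1 and 15.1.
- Missed if 25% to 100% go undetected: from 2.52 × 0.25 = 0.6 to 15.1.
- At 2% with half undetected: 252 × 0.02 × 0.5 = 2.5 missed, and the chance of at least one missed is 1 − (1 − 0.01)^252 = 0.92.

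**4. Effect on QALYs, if an unrecognised death were valued as alive.** Take a death at month 6 and an assumed utility of 0.3, 0.5 or 0.7.

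- QALY overcount per death: 0.5 × utility = 0.15, 0.25 or 0.35.
- Shift in the mean of an arm of 84: 0.15/84 = 0.002 to 0.35/84 = 0.004.
- Standard error of a difference between two arms of 84, with an assumed QALY SD of 0.1 to 0.25: SD × √(2/84) = 0.015 to 0.039.

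One unrecognised death moves an arm mean by well under one standard error, and equal numbers in two arms largely cancel. With 2% mortality and half undetected, the expected number missed is 0.84 per arm. The chance that two given arms differ by three or more is then about 5% (Poisson, equal rates). At 5% mortality with half undetected (2.1 per arm) it is about 21%.

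**The case against.** The strongest reply is that deaths are not left uncovered. The plan says that a cause of discontinuation will be established, provides a code for death, seeks consent to contact three trusted people and hospital staff, sends outreach workers to homes and shelters, audits charts, and requires prompt reporting of any death that staff learn of. All of that stands, and many deaths may be found this way. What does not follow is that a death will be told apart from non-contact: no source is assigned to that task, and code 1 is available whenever tracing fails.

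The 97 to 99 not seen are also not 97 to 99 of unknown vital status. The attrition section says that some will simply decline follow-up, and it calls the rates conservative. That is right, so the figure marks where visit-based capture stops, not how many deaths are missed.

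Three stronger readings are tempting and are not supported:

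- **Deaths are imputed as living.** The primary Cox analysis would mainly censor an unrecognised death. Multiple imputation is only sketched and is conditional on evidence of non-random dropout, and Aim 3b names no method. A positive utility after death is possible but not stated.
- **The restriction on the communication log keeps deaths out of the analysis.** It covers that log only. A death belongs on the SAE form and in the discontinuation record, which it does not touch.
- **Collection closes 30 days after the last attended visit.** The text does not say whether the last visit means attended or scheduled. The scheduled month-12 visit is an equally natural reading.

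**Conclusion.** The point holds as a gap in safety ascertainment. The plan names no source and no required check that separates death from inability to contact for the 38.5% to 39.3% projected unseen at month 12, so deaths among them can be absent from the comparison that the DSMB acts on. Analysts cannot reconstruct vital status later if nobody collected it. Unequal detection by arm is plausible given the peer contact in arm 1, but it is not demonstrated.

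How many deaths would be missed cannot be settled from the documents. The figures above rest on assumed mortality, detection, utility and SD. On those assumptions the effect on the QALY contrast is likely small, and no effect on the primary linkage conclusion has been shown. The separate silence on how death enters the Aim 1 and Aim 3b models is a wording gap that the same change can close. This is a cheap improvement worth making, not a flaw that undermines the trial.

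**What to change.** Under Collection and Reporting of SAEs and AEs:

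1. Record vital status (alive, dead with date, unknown) for every randomized participant at each missed visit and at month 12, using the locators and EHR access already planned.
2. Enter any death on the SAE form and under discontinuation code 9.
3. Count deaths to month 12 in the between-arm SAE comparison, whatever the last visit attended.

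In the analysis sections:

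4. Aim 1: end follow-up at the date of death by censoring, with death as a competing event in a sensitivity analysis, and impute nothing beyond that date.
5. Aim 3b: set utility to 0 from the date of death.

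The cost is one field on the tracing and EHR audit forms and a few sentences of analysis text. Some statuses will remain unknown; report their number by arm.
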